6.2.1.2. PK Concentration Analysis

- Analysis set: PK Concentration Set
- Analysis methodology:

Presentations for plasma PF-07265028 and serum sasanlimab will include:

- A listing of all concentrations sorted by dose, subject ID, cycle, and nominal time post-dose. The listing of concentrations will include the actual sample collection times, and the time of dosing. Deviations from the nominal time will be given in a separate listing.
- A summary of concentrations by dose, cycle, and nominal time post-dose, where the set of statistics will include n, mean, median, standard deviation, coefficient of variation (cv), minimum, maximum and the number of concentrations above the lower limit of quantification.
- Plots of median concentrations against nominal time post-dose by dose (based on the summary of concentrations by dose, cycle, and time post-dose), with all doses presented on the same plot. Two plots will be generated, so that the concentrations can be presented on linear and logarithmic scales.
- Plots of geometric mean concentrations against nominal time post-dose by dose (based on the summary of concentrations by dose, cycle, and time post-dose), with all doses presented on the same plot. Two plots will be generated, so that the concentrations can be presented on linear and logarithmic scales.
- Plots of individual concentrations against actual time post-dose (separate plots for each dose). Two plots per dose will be generated, so that the concentrations can be presented on linear and logarithmic scales.
- Plots of concentration against actual time post-dose by subject (separate line for each dose). Two plots per subject will be generated, so that the concentrations can be presented on linear and logarithmic scales.

For summary statistics and median plots by sampling time, the nominal PK sampling time will be used. For individual subject plots by time, the actual PK sampling time will be used. Exclusions or separate summaries for dose modifications and concomitant medications may be considered in data summaries.

- Missing data: missing concentration and BLQ values will be handled according to [Section 5.3.3](#).

6.2.2. Immunogenicity Analysis

- Analysis set: Immunogenicity Analysis Set.
- Analysis methodology:

For the immunogenicity data, the percentage of participants with positive ADA and Nab for each of sasanlimab combination dosing cohort will be summarized. For participants with positive ADA or neutralizing antibodies, the magnitude (titer), time of onset, and duration of ADA or neutralizing antibodies response will also be described, if data permit. The potential impact of immunogenicity on PK and CCI, safety/tolerability, and efficacy will be explored, if warranted by the data.

- Missing data: no imputed values will be derived.

6.2.3. Objective Response

In Part 1, objective response per RECIST 1.1 and irRECIST is a secondary endpoint. The proportion of participants with PR and irPR, as appropriate, will be derived.

- Analysis sets: Safety analysis set and response evaluable set, respectively.
- Analysis methodology:

Both confirmed ORR and unconfirmed ORR (uORR) will be determined based on the confirmed and unconfirmed CR and PR. ORR will be based on the best overall response (BOR) of a participant, according to RECIST 1.1 and irRECIST. In the BOR derivation, the minimum duration of SD as the best overall response is set as 5 weeks.

Unconfirmed CR (uCR) is defined as one objective status of CR documented before PD, while confirmed CR requires two objective statuses of CR a minimum of four weeks apart documented before PD. Sequences of CR - Non-evaluable - CR are considered confirmed CR as long as the two CR responses are observed at a minimum of 4 weeks apart. Similarly, unconfirmed PR (uPR) is defined as one objective status of PR documented before PD but not qualifying as uCR. Confirmed PR is defined as two objective statuses of PR or better (PR followed by PR or PR followed by CR) a minimum of four weeks apart documented before PD, but not qualifying as CR. Sequences of PR - Stable Disease or Non-evaluable - PR are considered PRs as long as the two PR responses are observed at a minimum of 4 weeks apart. Based on these definitions, the unconfirmed ORR analysis will include both confirmed CR or PR and unconfirmed CR or PR as responders, whereas the confirmed ORR analysis will only include confirmed CR or PR as responders.

Consider there may be some participants who cross over from Part 1A monotherapy to Part 1B combination therapy, two methods will be used for Part 1 ORR calculation. The primary one will only include (censor) the tumor response data by the cross over

date for those participants. The additional analysis will combine the participant who cross over from monotherapy to combination therapy with Part 1B participants for ORR calculation, in which only the tumor response data after the cross over date will be considered for the evaluation of best overall response. The re-baseline method may be considered if needed.

ORR and its 95% exact confidence interval as described in [Section 5.2.1](#) will be presented for each dose level and the total across all dose levels.

Tumor response will be presented in the form of participants data listings that include, but are not limited to: tumor type, actual received day 1 dose, tumor response at each assessment, and best overall response. Progression date, death date, date of first response, last assessment date, and date of last contact will also be listed.

- Additionally, a swimmer plot will be provided to display tumor response overtime and a waterfall plot displaying the best percentage change in tumor size will be provided. Missing data: missing tumor data will not be imputed.

CCI

6.3. Exploratory and Other Endpoints for Part 1

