The appearance of any new unequivocal malignant lesion indicates PD. If a new lesion is equivocal, for example due to its small size, continued assessment will clarify the etiology. If repeat assessments confirm the lesion, then progression should be recorded on the date of the initial assessment. A lesion identified in an area not previously scanned will be considered a new lesion.

Supplemental Investigations

- If CR determination depends on a residual lesion that decreased in size but did not disappear completely, it is recommended the residual lesion be investigated with biopsy or fine needle aspirate. If no disease is identified, objective status is CR.
- If progression determination depends on a lesion with an increase possibly due to necrosis, the lesion may be investigated with biopsy or fine needle aspirate to clarify status.

Subjective progression

Participants requiring discontinuation of treatment without objective evidence of disease progression should not be reported as PD on tumor assessment CRFs. This should be indicated on the EOT CRF as off treatment due to Global Deterioration of Health Status. Every effort should be made to document objective progression even after discontinuation of treatment.

Table 17. Objective Response Status at Each Evaluation

Target Lesions	Non-target Disease	New Lesions	Objective status
CR	CR	No	CR
CR	Non-CR/Non-PD	No	PR
CR	Indeterminate or Missing	No	PR
PR	Non-CR/Non-PD, Indeterminate, or Missing	No	PR
SD	Non-CR/Non-PD, Indeterminate, or Missing	No	Stable
Indeterminate or Missing	Non-PD	No	Indeterminate
PD	Any	Yes or No	PD
Any	PD	Yes or No	PD
Any	Any	Yes	PD

If the protocol allows enrollment of participants with only non-target disease, the following Table 18 will be used:

Table 18 Objective Response Status at each Evaluation for Patients with Non-Target Disease Only

Non-target Disease	New Lesions	Objective status
CR	No	CR
Non-CR/Non-PD	No	Non-CR/Non-PD
Indeterminate	No	Indeterminate
Unequivocal progression	Yes or No	PD
Any	Yes	PD

090177e198aafefApproved\Approved On: 22-Nov-2021 20:52 (GMT)

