2.1.2. Part 2 Primary Estimands

The treatment effect of PF-07265028 in combination with sasanlimab assessed by ORR using the RECIST version 1.1 and irRECIST in the analysis population.

- *Variable: Objective response defined as CR or PR according to RECIST v1.1 and irRECIST, from the date of first dose until the date of the first documentation of PD, death, or start of new anticancer therapy. Both CR and PR must be confirmed by repeat assessments performed no less than 4 weeks after the criteria for response are first met.*
- *Analysis population: The response evaluable set defined as all enrolled participants who received at least 1 dose of study treatment and had adequate baseline disease assessment. Participants who discontinued early or died will be included.*
- *Population-level summary measure: ORR defined as the proportion of participants in the analysis population with OR and 2-sided 95% CI for ORR using the Clopper-Pearson/Wilson method. Participants who do not have a post-baseline tumor assessment due to early progression of disease, who receive anti-cancer therapies other than the study treatments prior to reaching a CR or PR, or who die, have PD, or stop tumor assessments for any reason prior to reaching a CR or PR will be counted as non-responders in the assessment of OR.*

For the primary estimand of incidence of AEs, see [Section 2.1.1](#).

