6.4.1. Objective Response

OR is considered as a primary endpoint in Part 2. This endpoint in Part 2 will be analyzed in the same manner as described in [Section 6.2.3](#).

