6.5.1. Efficacy Endpoints

The secondary efficacy endpoints for Part 2 include multiple time-to-event endpoints such as DoR, PFS and OS.

- **Progression-Free Survival (PFS):** PFS will be summarized using the Kaplan-Meier method, as described in [Section 5.2.4](#). And PFS may also be displayed graphically when appropriate.

Participants without an event or with an event after 2 or more inadequate or missing tumor assessments will be censored on the date of the last adequate tumor assessment that documented no progression; deaths within 17 weeks after the first dose date for participants who did not initiate new anti-cancer therapy will still be considered an event. If a new anti-cancer therapy is started prior to an event, the participant will be censored on the date of the last adequate tumor assessment that documented no progression prior to the start of the new anti-cancer therapy.

Participants with no baseline tumor assessment (including participants with an inadequate baseline assessment) or with no adequate post-baseline tumor assessments within 17 weeks after the first dose date will be censored on the first dose date, unless the participant dies within 17 weeks of the first dose date, in which case, death will be an event on date of death.

PFS outcome and censoring rules are summaries in [Table 3](#). Any additional censoring rules that may affect data analysis will be documented in the Analysis Programming Specification (a separate document).

Any tumor scan or response data impacted by COVID-19 will be handled according to [Section 5.4](#).

Table 3. PFS and TTP Censoring Rules

Situation	Date of Event/Censoring	Outcome
No adequate baseline assessment	First dose date	Censored ^a
PD or death - after at most one missing or inadequate post-baseline tumor assessment, or - ≤ 17 weeks after the first dose date	Date of PD or death	Event
PD or death - after 2 or more missing or inadequate tumor assessments	Date of last adequate tumor assessment ^b documenting no PD prior to new anti-cancer therapy or missed tumor assessments	Censored
No PD		
New anti-cancer therapy given prior to PD or death		

a If the participant dies ≤ 17 weeks after the first dose date and did not initiate new anti-cancer therapy, the death is an event with date on death date.

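### The response definitions in SAP 6.2.3 stop only at progression, while the Part 2 primary estimand also stops at death or new anti-cancer therapy, so a response confirmed after new therapy starts could be counted

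*SAP*

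**What the plan says.** - **SAP 2.1.2, matching Protocol 9.1.1.3 (Part 2 primary estimand).** Objective response is counted "from the date of first dose until the date of the first documentation of PD, death, or start of new anticancer therapy". CR and PR need confirmation at least 4 weeks later. Participants given an outside anti-cancer therapy before they reach a CR or PR are non-responders.
- **SAP 6.2.3 (operational definitions).** For CR, "confirmed CR requires two objective statuses of CR a minimum of four weeks apart documented before PD". For the unconfirmed case, "unconfirmed PR (uPR) is defined as one objective status of PR documented before PD but not qualifying as uCR". Unconfirmed CR and confirmed PR have the same limit. None of the four definitions mentions death or new anti-cancer therapy. The section does set a date limit for one change of treatment, the crossover from Part 1A to Part 1B.
- **SAP 6.4.1.** For the primary objective response, "This endpoint in Part 2 will be analyzed in the same manner" as in 6.2.3.
- **SAP 6.5.1, Table 3.** The PFS rules have a row for "New anti-cancer therapy given prior to PD or death". It censors at the last adequate assessment before that therapy. DoR takes its outcomes and censoring reasons from PFS, apart from exceptions that do not matter here.
- **Protocol Appendix 12.** Under subjective progression: "Every effort should be made to document objective progression even after discontinuation of treatment".

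**The concern.** The estimand says which responses belong to the study treatment, and the derivation is what gets programmed. Here they differ on one intercurrent event, the start of another anti-cancer therapy before progression. The omission in 6.2.3 is easy to read as deliberate, because that section sets a cut-off for the Part 1A to 1B crossover and Table 3 names new therapy for PFS.

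At stake is the confirmed responder count in the Part 2 primary endpoint and in the Part 1 secondary endpoint. Any difference runs one way: the wider window can add confirmed responders but cannot remove them. ORR and DoR could also use different end dates for the same participant.

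**Working it through.** There is no stated figure to reproduce. The check compares the texts and then sizes one case.

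**1. The two rules by case**

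| Case | SAP 2.1.2 (Part 2) | SAP 6.2.3 read alone |
|---|---|---|
| First and confirming scans both before new therapy | Responder | Responder |
| First scan before, confirming scan after | Window and confirmation requirement point to exclusion; no sentence says so outright | Confirmed responder |
| First scan after new therapy, before PD | Non-responder, stated | Responder |

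The third row is settled for Part 2 by 2.1.2. The second is not, because the non-responder sentence speaks of reaching a CR or PR and does not say confirmed. Leaving death out of 6.2.3 has no practical effect, since no scan follows death.

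**2. Can the second row occur?** Scans are due every 8 weeks. Take a PR at Week 8, treatment stopped at Week 10, new therapy at Week 12, and an unscheduled scan at Week 16 that still shows PR.
- Protocol 8.1.1 asks for a withdrawal scan only if none was done in the previous 4 weeks. Here the gap is 10 − 8 = 2 weeks, so none is due.
- Protocol 8.2.8 asks for an end-of-treatment tumor assessment only if none was done in the last 8 weeks. Again none is due.
- The two PR assessments are 16 − 8 = 8 weeks apart, beyond the 4-week minimum, and no PD has been recorded. Under 6.2.3 this is a confirmed PR.
- Under 2.1.2 the window closed at Week 12 with the PR unconfirmed.

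The first PR lies in the window under both texts, so the unconfirmed ORR does not change. Only the confirmed ORR does.

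**3. DoR for the same participant.** Under Table 3 the last adequate assessment before new therapy is the Week 8 scan. DoR is censored there, on the day of first response and 8 weeks before the scan that confirmed it. The DoR text also has a general sentence censoring at the last available scan. This step takes Table 3 as governing, because the same bullet refers DoR censoring to the PFS rules.

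**4. irRECIST.** Response is assessed by RECIST 1.1 and irRECIST. Under Protocol Appendix 13, irPD needs a second observation at least 4 weeks later. A participant whose first irPD scan is never repeated, and who moves to another therapy, has no irPD. A limit set by progression alone then stays open.

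**5. Part 1.** Objective response is a secondary endpoint there, and Protocol 3.1 gives the secondary estimands as not applicable. SAP 2.1.2 is written for Part 2. Section 6.2.3 is therefore the only derivation, and it has no cut-off at outside therapy.

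**6. Size of one case.** A Part 2A cohort has up to 40 participants, and 1/40 = 2.5 percentage points. With assumed responder counts and Clopper-Pearson 95% intervals:
- 4/40 = 10.0% (2.8 to 23.7)
- 5/40 = 12.5% (4.2 to 26.8)
- 6/40 = 15.0% (5.7 to 29.8)

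The documents give no rate of new therapy before progression, so the expected number of cases cannot be calculated.

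**The case against.** The strongest reply is that the SAP should be read as a whole. Section 2.1.2 is the primary estimand in the same document, and 6.2.3 is silent on new therapy and does not overrule it. A reader might infer that a Part 2 response arising on the next therapy would be credited to the study drug. The documents do not support that, because 2.1.2 makes such a participant a non-responder. In the case left open, the tumor first responded on study treatment, and only the confirmation falls later.

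Exposure is also limited. Protocol 8.1.1 schedules tumor assessments up to withdrawal from treatment. Protocol 8.2.8 places end-of-treatment assessments before new anti-cancer therapy, and Protocol 8.2.9 makes the 60- and 90-day contacts remote by default. The Appendix 12 sentence concerns participants who stop without objective progression, and its purpose is to document progression. It is not a plan to scan responders on later therapy.

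These points limit the size of the problem. They do not settle the confirmation case, which no sentence in 2.1.2 addresses outright, and they supply nothing for Part 1. Appendix 12 also keeps post-treatment scans possible for participants who stop without recorded progression, whose window under 6.2.3 is still open.

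**Conclusion.** The inconsistency is real: a stated derivation rule has a wider window than the estimand it serves. In Part 2 the open case is a response first seen before new anti-cancer therapy and confirmed after it. In Part 1 the cut-off is missing altogether. A miscount is possible but not certain, since it requires 6.2.3 to be programmed literally and a post-withdrawal scan to be in the database. The number of cases is unknown and probably small. Each would move the confirmed ORR of a full 40-participant cohort by 2.5 points.

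A reader might also infer that one such case could decide the look at the first 15 participants, where enrollment may stop for minimal or no activity. The documents do not support that. In the open case the PR on study treatment is already visible activity, and that look is worded as an example with a permissive outcome, not as a rule based on confirmed ORR.

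**What to change.** In SAP 6.2.3, change the limit in the definitions of unconfirmed CR, confirmed CR, unconfirmed PR and confirmed PR from PD alone to the earliest of PD, death and the start of any anti-cancer therapy that is not a study treatment. State that, for a confirmed response, both the first and the confirming assessment must fall within that window, and cross-refer to 2.1.2. Leave the Part 1A to 1B crossover rule as it is; restricting the clause to non-study therapy keeps the crossover outside it.

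The cost is one clause and one date filter. SAP 6.5.1 already lists the date of follow-up anti-cancer therapy among the dates used for last contact, so no new data item should be needed. No design figure changes. The downside is that ORR may be slightly lower.

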6.3.1. Physical Examination

Participants will have physical examinations according to the study protocol. The physical examinations may include weight, vital signs, assessment of ECOG performance status and height, assessments of the cardiovascular, respiratory and gastrointestinal systems, skin, lungs etc. Physical examination generally will not be summarized or listed except vital signs or ECG. Any change from baseline considered by the investigation to be clinically significant should be recorded as an adverse event in the CRF, thus will be analyzed in the adverse events data.

6.3.2. Concomitant Medications and Nondrug Treatments

Concomitant, and further therapies (drug and non-drug treatments) will be coded by the World Health Organization (WHO) medical dictionary. This data will not be summarized. Data listings of concomitant medications and further therapies may be provided.

6.3.3. Exploratory Endpoints

For the tertiary and exploratory endpoints as described in Protocol Section 3, summary statistics will be presented. Results from tertiary/exploratory analyses will be reported in the CSR where possible. However, given the exploratory nature of exploratory objectives and endpoints, the analyses may not be complete at the time of the CSR. Results from exploratory analyses that are not included in the CSR are expected to be shared with the scientific

community through publication at a scientific conference and/or in a peer-reviewed scientific journal.

Detailed methodology for summary and statistical analyses of exploratory endpoints in this study will be further detailed in a biomarker statistical analysis plan (bSAP), which will be maintained by the sponsor.

6.4. Primary Endpoints for Part 2

6.4.1. Objective Response

OR is considered as a primary endpoint in Part 2. This endpoint in Part 2 will be analyzed in the same manner as described in [Section 6.2.3](#).

6.4.2. Safety Endpoints

Adverse events, laboratory tests, vital signs, and ECG including heart rate corrected QT interval are the safety primary endpoints for Part 2. The analysis set, analysis methodology will be same as described in [Section 6.1](#).

6.5. Secondary Endpoints for Part 2

6.5.1. Efficacy Endpoints

The secondary efficacy endpoints for Part 2 include multiple time-to-event endpoints such as DoR, PFS and OS.

- **Progression-Free Survival (PFS):** PFS will be summarized using the Kaplan-Meier method, as described in [Section 5.2.4](#). And PFS may also be displayed graphically when appropriate.

Participants without an event or with an event after 2 or more inadequate or missing tumor assessments will be censored on the date of the last adequate tumor assessment that documented no progression; deaths within 17 weeks after the first dose date for participants who did not initiate new anti-cancer therapy will still be considered an event. If a new anti-cancer therapy is started prior to an event, the participant will be censored on the date of the last adequate tumor assessment that documented no progression prior to the start of the new anti-cancer therapy.

Participants with no baseline tumor assessment (including participants with an inadequate baseline assessment) or with no adequate post-baseline tumor assessments within 17 weeks after the first dose date will be censored on the first dose date, unless the participant dies within 17 weeks of the first dose date, in which case, death will be an event on date of death.

PFS outcome and censoring rules are summaries in [Table 3](#). Any additional censoring rules that may affect data analysis will be documented in the Analysis Programming Specification (a separate document).

Any tumor scan or response data impacted by COVID-19 will be handled according to [Section 5.4](#).

Table 3. PFS and TTP Censoring Rules

Situation	Date of Event/Censoring	Outcome
No adequate baseline assessment	First dose date	Censored ^a
PD or death - after at most one missing or inadequate post-baseline tumor assessment, or - ≤ 17 weeks after the first dose date	Date of PD or death	Event
PD or death - after 2 or more missing or inadequate tumor assessments	Date of last adequate tumor assessment ^b documenting no PD prior to new anti-cancer therapy or missed tumor assessments	Censored
No PD		
New anti-cancer therapy given prior to PD or death		

a If the participant dies ≤ 17 weeks after the first dose date and did not initiate new anti-cancer therapy, the death is an event with date on death date.

b If there are no adequate post-baseline tumor assessments prior to the PD or death, then the time without adequate assessment should be measured from the first dose date; if the criteria were met the censoring will be on the first dose date.

- **Duration of Response (DoR):** DoR is defined as the time from first documentation of CR or PR to date of first documentation of PD or death due to any cause. The responders who have not disease progressed at the time of analysis will be censored at the last available tumor scan date. Both confirmed DoR and unconfirmed DoR (uDoR) will be determined separately for the subset of participants with a confirmed and unconfirmed objective response of CR or PR.

If there is a relatively large number of objective response, DoR may be analyzed using the Kaplan-Meier approach. The outcome, event dates and reasons for censoring for DoR will be the same as for those in the analysis of PFS except that participants will not be censored for inadequate baseline assessment or for no adequate post-baseline assessment, as only participants with an objective response are included in the analysis.

- **Overall Survival (OS):** OS will be analyzed with the Kaplan-Meier approach. Participants last known to be alive are censored at date of last contact. The date of last contact will be derived for participants not known to have died at the analysis data cutoff date using the latest complete date (non-imputed) among AE collection date, vital sign date, tumor assessment date, date of follow up anti-cancer therapy etc. This is not an exclusive list of possible dates. Any retrievable last contact date from the clinical database will be used.
- **Missing data:** For time-to-event endpoints, missing data will be handled by the censoring rules and no imputation will be performed.

